5. STUDY OBJECTIVES

5.1 PRIMARY OBJECTIVE

Our hypothesis is that patients with PVCs/VT who must undergo catheter ablation can benefit from a VIVO non-contact mapping and guided ablation in terms of efficacy to decrease the procedural time of the ablation and acute success.

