6. STUDY DESIGN

6.1 OVERALL DESIGN

This is a prospective, single arm, observational and feasibility study, which will recruit 15 non-selected patients, with structurally normal heart, with a conventional indication for catheter ablation of PVCs/VT. The follow up will be of three months. The study will also include another retrospective cohort, including age & gender matched patients, without cardiac structural disease, with a conventional indication for catheter ablation of PVCs/VT from the last 5 years' database of the same operator. For this second retrospective cohort there will be no follow-up.

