10.3 TREATMENT PROCEDURE

Using the roadmap 3D image information of the CMR or CT scan a standard three-dimensional (3D) reconstruction will be performed (CARTO software package). The CMR or CT scan will be also imported into the Vivo anatomy software to reconstruct the patient's model, necessary for the following localization analysis.

Before the start of the ablation procedure, when still in the ward, the patient will undergo a 12-lead ECG recording (Mortara) while contemporarily on telemetry in order to record the templates of the different PVC/VT morphologies, with also regards to their frequency. Should the patient present no ventricular arrhythmia, a challenge with exercise bike or

intravenous administration of isoprenaline or atropine could be chosen. Finally, a picture of the patient's chest will be taken and imported in the software to match the ECG electrodes' position.

Mapping Vivo non-contact system and ablation procedure

Once the different templates are acquired, they will be imported into the VIVO analysis system, and a final model with foci localization will be generated. The information will be integrated into the 3D mapping system prior to starting the procedure.

After venous vascular access has been gained using an ultrasound-guided approach, an octapolar catheter (Inquiry™, Saint Jude Medical) will be positioned in His-RV position, while a mapping/ablative catheter will be used both for mapping and RF delivery. In case of arrhythmias originating from the LV, it is the operator's choice to use either an arterial femoral access for a retrograde approach or a transseptal access route. In case of left-sided access, as per institutional standard, ACT measurements will be carried out every 30 min with bolus injections of Heparin to achieve an ACT of ≥ 350 sec.

The whole ablative procedure will be carried out according to international guidelines and as for operator expertise and discretion. Achievement of PVC/VT suppression will be documented for all patients for 30 minutes after last RF delivery, with or without IV drug provocation challenge. DCCV may be carried out at the discretion of the operator during the procedure if needed.

Removal of sheaths will be performed as per institutional standard (+/- protamine).

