14.1 SAMPLE SIZE AND RECRUITMENT

This is a feasibility pilot study, which will test the feasibility of PVC/VT foci mapping with Vivo system and catheter ablation in unselected patients without structural heart disease, eligible for PVC/VT ablation. Therefore, no power calculation has been done and the number of patient recruited will be of 15 which are deemed sufficient by the CI and Co-PIs on a clinical basis.

The estimated recruitment period for the trial will be of 6 months. We estimate that this sample size is attainable in practice, as the number of PVC/VT ablation procedures per year performed within the Trust is around 100. We also included patients with previous PVC/VT ablation in order to maximise chances of recruitment. This pilot is performed with the intention to plan a prospective multi-operator/multicentre trial which is adequately powered. We will aim to compare the procedure parameters as well as the outcome of this trial to age & gender matched procedures of the same operators from the last 5 years' database.

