14.2.2 Secondary endpoints

- To assess clinical outcome (suppression of reduction of PVCs burden/VT at 3 months F/U)
- To assess safety
- To assess economical outcome (cost reduction per case)

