14.3 STATISTICAL ANALYSIS PLAN

Descriptive statistic data with regard to baseline and procedural variables will be reported; continuous variables will be expressed by mean \pm standard deviation or median and interquartile range (25th, 75th percentile), depending on the normality of distribution; categorical variables will be summarized by frequencies and percentages. The outcome of radiofrequency ablation on the entire cohort of patients will be presented in the form of percentage of patients free from symptomatic or documented arrhythmia or with only mild symptoms related to arrhythmia recurrence.

Depending on the severity of symptoms and documentation of tachycardia during follow-up, patients will be divided into two groups (success/recurrence). Baseline characteristics and procedural variables will be compared between these two groups by student t-tests, Mann Whitney U tests, or Fisher's exact test where appropriate in order to identify those variables associated with better mid/long term outcomes. A two-tailed p value <0.05 will be considered statistically significant. Intra-patient improvement from baseline to 6 months follow-up visit will be assessed by McNemar's test. Freedom from PVC/VT will be assessed as a time-dependent variable using Cox proportional hazard models.

To judge if ablation strategy using Vivo mapping system is as successful in achieving the clinical endpoint, we will compare the procedure parameters as well as the outcome of this trial to age & gender matched procedures of the same operator from the last 5 years' database.

To measure the strength of association between the acute successes (PVC/VT suppression at the end of the ablation) and outcome, a McNemar test will be performed. Data will be analyzed using SPSS version 18 (IBM Corporation).

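### The plan compares an undefined clinical endpoint with historical controls, and on the likelier 3-month reading section 6.1 plans no follow-up for those controls

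*Combined protocol and SAP*

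**What the plan says.** All references are to the combined protocol and SAP.

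- **The comparison.** Section 14.1: "We will aim to compare the procedure parameters as well as the outcome of this trial to age & gender matched procedures". Section 14.3 repeats this and gives the purpose: "To judge if ablation strategy using Vivo mapping system is as successful in achieving the clinical endpoint". Section 14.3 is the only place where the term clinical endpoint appears, and it carries no definition.
- **The controls.** Section 6.1 describes a retrospective cohort from the operator's database of the last 5 years and adds: "For this second retrospective cohort there will be no follow-up". The VIVO cohort is followed for three months.
- **The nearest listed endpoint.** Section 14.2.2: "To assess clinical outcome (suppression of reduction of PVCs burden/VT at 3 months F/U"). Section 14.3 reports the result of ablation as the "percentage of patients free from symptomatic or documented arrhythmia or with only mild symptoms related to arrhythmia recurrence", and sorts patients into success or recurrence from what happens during follow-up.
- **Acute success.** Section 5.1 states the hypothesis of benefit "in terms of efficacy to decrease the procedural time of the ablation and acute success". Section 10.3 says: "Achievement of PVC/VT suppression will be documented for all patients for 30 minutes after last RF delivery". Acute success is not among the endpoints listed in section 14.2.
- **The frame.** The opening of section 14 says that procedural outcomes will be compared with the matched procedures and that the design is descriptive only.
- **The 3-month assessments.** The charts in sections 6.3 and 10.5 mark the 12-lead ECG as routine and list an EP outpatient visit. They mark the Mortara Holter and the symptom questionnaire as research.

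**The concern.** A comparison of outcomes needs the outcome in both cohorts, measured in the same way. If the clinical endpoint is the 3-month result, the plan provides for it in the VIVO cohort and makes no stated provision for it in the controls.

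An analyst who followed the text would have to drop the comparison or use whatever the old records hold. In the second case, a recurrence seen on a research Holter in a VIVO patient might have gone unrecorded in a control. Unequal detection would add to the confounding that any historical comparison carries, and would probably make VIVO look worse than it is. Section 14.1 says the pilot is meant to lead to an adequately powered multicentre trial, so a distorted comparison could carry forward into its planning.

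**Working it through.** The plan states no success rate, number of controls, margin or power for this comparison, so there is no figure to reproduce. The check is mainly one of text.

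**Step 1. What does the clinical endpoint mean?**

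*For the 3-month outcome:*
- Section 14.2.2 places clinical outcome at 3 months.
- Section 14.3 assigns success or recurrence from follow-up data.
- Sections 14.1 and 14.3 name the outcome in addition to procedure parameters, so it is something more than procedural data.
- Directly after the comparison, section 14.3 plans a further analysis: "To measure the strength of association between the acute successes (PVC/VT suppression at the end of the ablation) and outcome". This treats acute success and outcome as two different things.

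*For an acute or procedural result:*
- Section 5.1 puts acute success in the primary hypothesis, and section 10.3 ensures that it is recorded.
- The opening of section 14 speaks of procedural outcomes, though it does not say that only these will be compared.
- Section 5.2 attaches the comparison with historic controls to procedure time and cost.

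The 3-month reading is the likelier, but the text does not settle it.

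**Step 2. Does each reading fit section 6.1?**
- Acute or procedural reading: yes. The procedure record is enough, and the only defect is an undefined term.
- 3-month reading, with section 6.1 meaning no data after the procedure: no. The controls have no outcome to compare.
- 3-month reading, with section 6.1 meaning no study visits: possibly. Routine ECG and clinic records may exist, but no section says that they will be abstracted, what they contain or how the outcome was measured.

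**Step 3. Could ascertainment differ?** Section 10.5 has recurrence assessed by the Mortara Holter. That Holter and the questionnaire are research items, so controls cannot be assumed to have equivalents. If true recurrence *r* is the same in both cohorts, the apparent difference from detection alone is

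gap = *r* × (detection in VIVO − detection in controls),

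where a positive gap means that VIVO looks worse. None of these inputs is in the documents. With assumed *r* of 10% to 30%, detection of 80% to 100% in VIVO and 50% to 90% in controls:
- lowest: 0.30 × (0.80 − 0.90) = −3 points
- a middle case: 0.20 × (0.90 − 0.70) = +4 points
- highest: 0.30 × (1.00 − 0.50) = +15 points
- equal detection: 0

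The assumptions set detection mostly lower in controls, so the direction is largely an input. The formula shows how the bias would arise. It does not estimate it.

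**Step 4. Could 15 patients support a judgement of equal success?** This is a separate matter from the conflict, but it bears on the wording. With an assumed 15 controls and equal success *p*, the approximate 95% half-width for the difference is 1.96 × √[*p*(1 − *p*)(1/15 + 1/15)]:
- *p* = 0.70: 32.8 points
- *p* = 0.80: 28.6 points
- *p* = 0.90: 21.5 points, which is too narrow to trust at this size

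Newcombe intervals with equal observed counts give about ±29.8 points at 11/15, ±28.3 at 12/15 and ±26.4 at 13/15. This imprecision comes from the sample size and would remain if the controls had perfect follow-up.

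**The case against.** The strongest reply is that the conflict depends on two readings, neither of them certain. For a retrospective database cohort, a statement that there will be no follow-up most naturally means no new visits, which does not bar the use of past records. The schedule helps this reply: the 3-month ECG is routine and an EP outpatient visit is listed, and section 7.3 says that withdrawn patients continue to be seen regularly in the arrhythmia clinic. Earlier patients of the same operator may well have comparable records. The comparator is also described throughout as procedures, and the opening of section 14 uses nearly the same phrase for procedural outcomes. Finally, the study is openly an unpowered, descriptive pilot, and no test or margin is attached to this comparison.

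Much of this stands. A reader might infer that the controls certainly have no 3-month data and the comparison is impossible. The documents do not support that. A reader might also take the +15 points above, or the wide intervals, as the size of the defect. The first rests wholly on assumed detection rates, and the second reflects 15 patients.

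The reply does not remove the point. No section says that the database holds 3-month outcomes or that they will be abstracted, the main recurrence measure is a research item, and the separation of acute success from outcome in section 14.3 keeps the 3-month reading the likelier one.

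**Conclusion.** The point holds in a conditional form. The clinical endpoint is undefined. On its likelier 3-month meaning, the planned comparison has either no control data or control data not shown to have been ascertained as in the VIVO cohort, and sections 14.1 and 14.3 conflict with section 6.1. On the acute or procedural meaning, the fault is only a missing definition.

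The size of any bias cannot be derived from the documents. The likely direction is against VIVO, on the assumption that the research Holter and questionnaire detect more than routine records do.

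The consequences are limited. On the 3-month reading this is a secondary endpoint in a descriptive pilot. It would be wrong to infer that the primary efficacy comparison is compromised in this way, because procedure time needs no follow-up. It would also be wrong to read section 14.3 as a formal non-inferiority claim, since it sets no margin. The text should still be corrected before analysis, because the plan as written cannot be carried out without a decision that it does not record.

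**What to change.** Define the clinical endpoint (measure, threshold and time point), and reconcile sections 6.1, 14, 14.1 and 14.3 with that definition.

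**Preferred.** Limit the historical comparison to procedural parameters and acute success taken from the procedure record. Report the 3-month outcome for the VIVO cohort alone with an exact (Clopper-Pearson) 95% confidence interval. For illustration, 12 successes in 15 would give 52% to 96%. The cost is a change of wording and a more modest secondary conclusion.

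**Alternative.** State in section 6.1 that routine post-procedure records will be abstracted for controls, and say what they hold and how the outcome was measured. Compare only on an outcome ascertained in the same way in both cohorts, for example from the routine ECG and clinic visit, leaving out the research Holter and questionnaire. Report how many controls have such data, give the difference with a 95% confidence interval, and label it exploratory. The cost is some chart abstraction, and the richer VIVO data are not used between cohorts.

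**In either case,** replace the stated purpose in section 14.3 with a descriptive one, such as: *to describe procedural parameters and the defined outcome alongside those of matched historical procedures*. Under the preferred option, the defined outcome in that sentence is acute success.

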14. STATISTICAL DESIGN

This is a prospective, non-randomised, observational study which will recruit 15 non-selected patients with PVC/VT eligible for catheter ablation, without structural heart disease.

Procedural outcomes will be compared to age & gender matched procedures of the same operator from the last 5 years' database.

The statistical design was decided in collaboration with the study PIs and will be descriptive only.

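### Section 14.3 uses McNemar's test to measure association between acute success and later outcome, but the test only compares two paired success rates

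*Combined protocol and SAP*

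**What the plan says.** The last paragraph of section 14.3 gives aim and method together: "strength of association between the acute successes (PVC/VT suppression at the end of the ablation) and outcome, a McNemar test will be performed". It names no measure of association for this question, such as a risk difference, odds ratio or phi.

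Other parts of the plan bear on it:

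- Section 14.3 splits patients into success and recurrence groups and compares baseline and procedural variables between them by "student t-tests, Mann Whitney U tests, or Fisher's exact test where appropriate in order to identify those variables associated with better mid/long term outcomes".
- Section 14.3 also uses McNemar for a before-and-after question: "Intra-patient improvement from baseline to 6 months follow-up visit will be assessed by McNemar's test".
- Section 14.3 sets a threshold: "A two-tailed p value <0.05 will be considered statistically significant".
- Section 14 says the statistical design "will be descriptive only".
- Section 10.3 provides the acute variable: "Achievement of PVC/VT suppression will be documented for all patients for 30 minutes after last RF delivery".
- Section 14.1 gives the size: "no power calculation has been done and the number of patient recruited will be of 15".

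No other section corrects or qualifies the McNemar sentence.

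**The concern.** The question asked is whether patients with acute suppression do better later than patients without it. That compares the rows of a 2x2 table of acute result by outcome. McNemar compares the table's two margins: the proportion successful at the end of the procedure and the proportion successful at follow-up. The two questions are different and can have opposite answers.

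The result could mislead in either direction. A significant McNemar result may show only that some initially successful patients recurred, yet be reported as an association. A strong association with little net change in the success rate would be reported as absent.

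Acute success is part of the hypothesis in section 5.1, and section 14.1 says the pilot is meant to lead to an adequately powered multicentre trial. Whether acute suppression tracks later outcome is relevant to choosing endpoints for that trial.

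**Working it through.** The plan states no result or power for this analysis, so there is no figure to reproduce. The check asks whether McNemar responds to association at the planned size.

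**Inputs from the documents.** N = 15 (14.1). Two-sided 0.05 (14.3). Acute success yes/no for every patient (10.3). Outcome success/recurrence (14.3).

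**Assumptions.** All cell counts and success rates below are assumed, because the documents give none. The exact two-sided form of McNemar is used.

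**Notation.** a = acute success, later success; b = acute success, recurrence; c = acute failure, later success; d = acute failure, recurrence.

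- McNemar: p = 2 × P(Bin(b + c, 0.5) ≥ max(b, c)), capped at 1. The cells a and d do not enter.
- Phi: (ad − bc) / √[(a+b)(c+d)(a+c)(b+d)]. All four cells enter.

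**Step 1: single tables with N = 15.**

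| (a, b, c, d) | Phi | McNemar p | Fisher p |
|---|---|---|---|
| (12, 0, 0, 3) | 1.00 | 1.00 | 0.0022 |
| (0, 7, 8, 0) | −1.00 | 1.00 | 0.0002 |
| (4, 8, 1, 2) | 0.00 | 0.039 | 1.00 |

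In the first table b + c = 0, so McNemar has nothing to test, while Fisher gives 1/C(15,3) = 1/455 = 0.0022. In the third, later success is 4/12 after acute success and 1/3 after acute failure, which are identical, and ad − bc = 8 − 8 = 0. McNemar still gives 2 × (9 + 1)/512 = 0.039, because 8 of the 9 discordant patients went from success to recurrence.

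**Step 2: hold the discordant cells fixed.** With b = 6 and c = 0, moving a from 1 to 8 leaves McNemar at 0.031 while phi ranges from 0.29 to 0.43. With b = c = 2, moving a from 0 to 11 leaves McNemar at 1.00 while phi ranges from −0.15 to 0.46.

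**Step 3: how often p < 0.05 when there is no association.** All 816 possible tables with N = 15 were enumerated with multinomial weights, taking acute success and outcome as independent.

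| Acute / follow-up success | McNemar | Fisher |
|---|---|---|
| 0.8 / 0.8 | 0.8% | 0.9% |
| 0.9 / 0.8 | 1.7% | 0.5% |
| 0.8 / 0.7 | 2.9% | 1.2% |
| 0.9 / 0.7 | 9.4% | 0.5% |
| 0.8 / 0.6 | 10.0% | 1.3% |
| 0.9 / 0.6 | 26% | 0.4% |
| 0.9 / 0.5 | 49% | 0.4% |
| 0.9 / 0.4 | 72% | 0.4% |

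**Step 4: how often p < 0.05 when the association is strong.** Follow-up success is taken as 90% after acute success and 10% after acute failure.

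| Acute success | McNemar | Fisher |
|---|---|---|
| 0.6 | 0.01% | 88% |
| 0.7 | 0.03% | 80% |
| 0.8 | 0.06% | 61% |
| 0.9 | 0.12% | 28% |

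**Step 5: when no method can help.** If all 15 patients have acute success, association cannot be estimated. The probability is 0.8^15 = 3.5% or 0.9^15 = 21%.

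**The case against.** The strongest defence has four parts.

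1. **The stakes are low.** The analysis is tied to no listed endpoint, in an unpowered pilot whose statistics are declared descriptive. No decision in the plan depends on this p-value. This stands and limits the weight of the point. It does not remove it, because 14.3 also sets a 0.05 threshold, and even a descriptive reading needs an effect measure that the plan does not give.

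2. **A suitable test may already be planned.** Acute suppression can be read as a procedural variable, and so fall under the Fisher comparison of success and recurrence groups. That is a fair reading, but the plan then names McNemar for this question. At best, two tests that can disagree completely are applied to the same table.

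3. **The wording may be at fault, not the test.** McNemar is valid for these paired data if the question is whether success falls between the end of ablation and follow-up. That may be what the authors meant. It is not what the text says, so either the aim or the test has to change.

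4. **The size depends on chosen scenarios, and Fisher will often find nothing either.** This stands. If success drops by 10 points or less, McNemar's rate in Step 3 is only 0.8% to 2.9%. With a moderate association (75% against 25% later success) and acute success of 0.9, McNemar reaches p < 0.05 in 7.6% of trials and Fisher in 7.4%; at acute success 0.95, Fisher does so in 2.0%. Similar rejection rates still do not make McNemar a test of association, and low precision is a reason to report an estimate with its interval.

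**Conclusion.** The point holds: the test named in 14.3 does not answer the question stated in the same sentence. Steps 1 and 2 show this from the form of the test, without assuming any success rate.

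The practical size does depend on unknown rates. Under independence, McNemar's chance of a significant result runs from under 1% when the success rate does not fall to 72% when it falls from 90% to 40%. Under the strong association assumed, it detects almost nothing (at most 0.12%).

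The sentence should be corrected before analysis. The consequence is confined to a supporting analysis, and no primary or secondary endpoint in 14.2 changes. Correcting it makes the result mean what it claims; with 15 patients and probably few acute failures, the estimate will still be imprecise.

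**What to change.** Replace the McNemar sentence in 14.3 with, for example: *Acute success by 3-month outcome will be reported as a 2x2 table, with the risk difference and its exact 95% confidence interval. Fisher's exact test will be used if a p-value is given. The interval is expected to be wide with 15 patients and is descriptive. If all patients have acute success, the association will be reported as not estimable.*

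The risk difference is preferable to an odds ratio as the main measure, because an empty cell is likely here and makes the odds ratio zero or infinite. The 3-month time point follows sections 6.1, 10.4 and 14.2.2; the reference to 6 months elsewhere in 14.3 should be reconciled with it. The same edit should state which success/recurrence definition is used, since 14.3 relies on symptoms and documented tachycardia while 14.2.2 refers to PVC burden.

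If the authors meant to ask whether the success rate changes from the end of the procedure to follow-up, they should keep McNemar, state that purpose, and report the paired difference in success rates.

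Either version is a one-sentence change, with no extra data and no burden on patients. Both variables are already planned for collection.
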